5.6 Unscheduled Visit

Unscheduled visits may be necessary to repeat testing following abnormal laboratory results, for follow-up of AEs, or for any other reason, as warranted in the judgement of the Investigator.

The following information will be collected for all subjects:

- Concomitant medications/procedures
- AEs
- BSA, IGA, HESCI

5.7 Adverse Events

5.7.1 Adverse Event Definition

An AE means any untoward medical occurrence associated with the use of a drug in humans, whether or not considered drug related. An AE can therefore be any unfavorable and unintended sign (including an abnormal laboratory finding), symptom, or disease temporally associated with the use of a medicinal (investigational) product, whether or not related to the medicinal (investigational) product.

AEs will be collected following informed consent of the subject through subject study completion.

A treatment emergent adverse event (TEAE) is defined as an AE that started post application of investigational product through study completion.

Application site reactions will be considered adverse events if they require intervention, suspension or discontinuation of investigational product.

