5.7.5 Adverse Event Reporting

AEs will be collected following informed consent of the subject through subject study completion.

The Investigator will review each event and assess its relationship to investigational product treatment (unrelated, unlikely, possibly, probably, likely). Each sign or symptom reported will be graded on the NIH NCI CTCAE (Version 5.0) toxicity grading scale 5-point severity scale (Grade 1, 2, 3, 4 and 5). The date and time of onset, time relationship to drug dosing, duration, and outcome (resolved, improved, unchanged, worse, fatal, or unknown/lost to follow-up) of each event will be noted.

The relationship of each AE to the investigational product will be assessed using the following definitions:

Unrelated	
 The AE must clearly be caused by the subject’s clinical state, or the study procedure/conditions. Definitely not related to drug. Temporal sequence of AE onset relative to administration of drug not reasonable. Another obvious cause of an AE.
Unlikely	
 Time sequence is unreasonable. There is another more likely cause for an AE.
Possibly	
 Corresponds to what is known about the drug. Time sequence is reasonable. Could have been due to another equally, likely cause.
Probably	
 Is a known effect of the drug. Time sequence from taking drug is reasonable. Ceases on stopping the drug. Cannot be reasonably explained by the known characteristics of the subject’s clinical state.
Likely	
 Is a known effect of the drug (e.g., listed in Physicians' Desk Reference, Compendium of Pharmaceuticals and Specialties, IB). Time sequence from taking drug is reasonable. Event stops upon stopping drug, event returns upon restarting drug.

The following CTCAE toxicity grading scale 5-point severity scale definitions for rating maximum severity will be used:

Grade 1	Mild; asymptomatic or mild symptoms; clinical or diagnostic observations only; intervention not indicated.
Grade 2	Moderate; minimal, local or noninvasive intervention indicated; limiting age-appropriate instrumental activities of daily living.*

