6.3.1 Adverse Events

All treatment-emergent AEs occurring during the study will be recorded and classified on the basis of MedDRA terminology for the safety population. Treatment-emergent AEs are those AEs with an onset on or after the date of study treatment. All treatment-emergent AEs will be summarized by treatment group, the number of subjects reporting treatment-emergent AEs, system organ class, preferred term, severity, relationship, and seriousness. Serious adverse events (SAEs) will be listed by subject. SAEs will be summarized by treatment group, severity, and relationship to study treatment. For AEs, each subject will be counted only once within a system organ class or a preferred term using the event with the greatest relationship and greatest severity.

All information pertaining to AEs noted during the study will be listed by subject, detailing the verbatim description given by the Investigator, preferred term, system organ class, start date, stop date, severity, action taken regarding IP, corrective treatment, outcome, and IP relatedness. The event onset will also be shown relative (in number of days) to date of first application.

In addition, a listing of subjects who prematurely discontinued from the IP due to adverse events will also be provided.

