- **Number of Expected IP Applications (BID dosing)** = 170 (Cohort 2 BID) for subjects who complete the study or number of days between first and last application of IP, derived as  $2 * (\text{last treatment date} - \text{first treatment date} + 1)$ , for subjects who discontinue early from the study.
- **Number of Expected IP Applications (QD dosing)** = 30 (Cohort 1) or 85 (Cohort 2 QD) for subjects who complete the study or number of days between first and last application of IP, derived as  $(\text{last treatment date} - \text{first treatment date} + 1)$ , for subjects who discontinue early from the study.
- **Number of IP Applications** = number of expected IP applications – missed IP applications as collected in the electronic case report form (eCRF).
- **Weight of IP (g)** = returned tube weight – dispensed tube weight.
- **Body Mass Index (BMI) ( $\text{kg}/\text{m}^2$ )** =  $[\text{weight (kg)} / \text{height (cm)} / \text{height (cm)}] \times 10,000$ .
- **Change from Baseline** = value at current time point – value at baseline.
- **Treatment Emergent AE (TEAE)** = any AE with an onset date/time after the first application of IP. If time is unavailable, any AE occurring on or after the date of first application of IP will be considered treatment emergent.
- **Completion of Study** = Completion of the primary efficacy assessment (IGA) at Week 12. This may differ than what was recorded in the eCRF.

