### 9.1. Adverse Events

All AEs, TEAEs, and SAEs will be coded using the MedDRA dictionary version 23.0.

A TEAE is defined as an AE within an onset on or after the day of study treatment through study completion. An overall summary of TEAEs will be provided; this will present number and percent of subjects who reported at least 1 of the following: TEAE (including all TEAEs, TEAEs by maximum severity, and related TEAEs), SAE, discontinued the study due to a TEAE, discontinued the study drug due to a TEAE, or a TEAE resulting in death.

The number and percent of subjects reporting TEAEs, grouped by MedDRA system organ class (SOC) and preferred term, will be tabulated by severity or by greatest relationship to study drug and treatment group within cohort. In the case of multiple occurrences of the same TEAE within the same subject, each subject will only be counted once for each preferred term. Additionally, the number and percent of subjects reporting related TEAEs will be summarized by MedDRA SOC, preferred term, severity, and treatment group within cohort.

Relationship to study drug will be mapped as follows: related = likely related, probably related, or possibly related; unrelated = unlikely related or unrelated. In the summaries showing severity and relationship to study medication the event with the maximum severity (mild < moderate < severe < life-threatening < death) or strongest relationship (unrelated < related) will be reported. If a particular event is missing the severity and/or relationship, then the strongest possible severity or relationship will be assumed for analysis (severity = severe, relationship = related).

In the AE data listings, all AEs will be displayed. Any AEs that are treatment emergent will be flagged.

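### TEAEs are defined by onset only, so a non-serious AE that starts between consent and first application and then worsens on the cream is left out of the TEAE tables

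*Protocol*

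**What the plan says.** Four places define a treatment-emergent AE.

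- Protocol 5.7.1: "A treatment emergent adverse event (TEAE) is defined as an AE that started post application of investigational product through study completion".
- Protocol 6.3.1: "Treatment-emergent AEs are those AEs with an onset on or after the date of study treatment".
- SAP 6.1.7: "any AE with an onset date/time after the first application of IP", with a fallback: "If time is unavailable, any AE occurring on or after the date of first application of IP will be considered treatment emergent".
- SAP 9.1: "A TEAE is defined as an AE within an onset on or after the day of study treatment through study completion".

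The footnotes to the AE table shells, to Table 14.3.3.1 and to Listing 16.2.7.1 repeat the SAP 9.1 rule.

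On collection, protocol 5.7.5 says "AEs will be collected following informed consent of the subject through subject study completion". On grading, the same section says that the CTCAE "severity scale definitions for rating maximum severity will be used".

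SAP 9.1 and 9.1.1 limit the severity, relationship and withdrawal summaries to TEAEs. The SAP also plans a listing of all AEs with TEAEs flagged, a listing of AEs that led to withdrawal of study drug, and SAE tables with no stated restriction to TEAEs (SAP 9.1, 9.1.1 and 9.1.2).

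**The concern.** Screening can last 4 weeks and AEs are recorded throughout it, so some subjects can reach Day 1 with an AE already on the database. If that AE becomes more severe on the cream, the change is an on-treatment safety event. A rule based on onset alone does not count it.

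The error runs in one direction. It never adds a TEAE; it can only drop a worsening. AE incidence and severity are part of the Cohort 1 primary endpoint (protocol 3.2.1) and are safety endpoints in Cohort 2 (SAP 2.2.2). This is also the first human study of the cream (protocol 2.3). The oral drug showed thyroid, liver-enzyme and urinary-infection signals (protocol 2.3.1 and 2.4.1), and findings of that kind can be present before dosing and progress later.

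**Working it through.** The documents give no figure to reproduce, so the check is textual.

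**Step 1: do the definitions contain a worsening clause?**

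| Place | Test applied | Worsening of a pre-dose AE |
|---|---|---|
| Protocol 5.7.1 | started after application | not covered |
| Protocol 6.3.1 | onset on or after the treatment date | not covered |
| SAP 6.1.7 | onset date/time after first application | not covered |
| SAP 6.1.7 fallback | onset time unavailable: on or after the date of first application | not covered |
| SAP 9.1 and footnotes | onset on or after the treatment day | not covered |

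The rows differ on how they treat Day 1 before the application. That is a separate inconsistency. All of them exclude an AE that began in screening.

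**Step 2: is there a recording rule that would give the worsening a post-dose onset?** Protocol 5.7.5 rates maximum severity and says nothing about a new record when the grade rises. The one partial route is protocol 6.3.3, under which clinically significant physical-examination changes become AEs. That examination covers skin, lungs and heart only (protocol 5.1.3). In Cohort 2 the only scheduled examination after baseline is at Week 12 (protocol 1.3).

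**Step 3: which outputs lose the event and which keep it?** Take a non-serious AE with onset between consent and first application, a grade increase on treatment, and no new record.

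| Output | Event shown? |
|---|---|
| Table 14.3.1.1, TEAE rows | No |
| Tables 14.3.1.2 to 14.3.1.8 | No |
| Listing 16.2.7.1 (all AEs) | Yes, not flagged as a TEAE |
| Table 14.3.3.1 (AEs leading to study drug discontinuation) | Yes, if study drug was stopped for it |
| Table 14.3.1.1 SAE row; Tables 14.3.2.1 to 14.3.2.3 | Only if serious |

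The listing shells carry one grade per record. With a single record, a reader cannot tell whether the maximum grade was reached before or after dosing.

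**Step 4: size, under assumed rates only.** Suppose 5% to 15% of subjects have an AE recorded before the first application, and 5% to 20% of those worsen on treatment. Neither rate comes from the documents.

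- Share affected: 0.05 × 0.05 = 0.25% to 0.15 × 0.20 = 3%.
- Cohort 2: 215 × 0.0025 = 0.54 to 215 × 0.03 = 6.45 subjects.
- Arm of 61 at the upper end: 61 × 0.03 = 1.8. Arm of 31: 31 × 0.03 = 0.9.
- One subject in an arm of 31: 1/31 = 3.2%.
- Cohort 1: 6 × 0.0025 = 0.015 to 6 × 0.03 = 0.18 subjects.

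**The case against.** The strongest reply is that little is lost. The all-AE listing keeps the event. The discontinuation listing has a TEAE column and is not restricted to TEAEs. Serious events still enter the SAE tables and the SAE row of Table 14.3.1.1. All of this stands. A reader might infer that such worsening disappears from the report, and the documents do not support that: it is missing from the TEAE summaries.

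A reader might also infer that any pre-existing condition that worsens is uncounted. That goes too far. A condition present before consent is medical history (protocol 5.1.1), and its worsening on treatment can be recorded as a new AE with a post-dose start. Significant active infection at entry is excluded (protocol 4.7.2, criterion 8). The gap is limited to onset between consent and first application.

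Nor do the documents say that each event has exactly one record. They are silent, and entry conventions may sit in CRF instructions that are not available here. The exclusion is therefore conditional on site practice. That is a weakness in itself, because whether an event counts then depends on an unwritten habit.

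The laboratory stopping rule in protocol 4.10 might look like a ready illustration. It is not a clean one, because that rule itself uses the term treatment-emergent.

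Laboratory values are summarised separately as change from baseline with minimum and maximum (SAP 9.3). The shift tables use only low, normal and high, so a rise in grade within the high category does not show there.

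Finally, SAP 9 plans no inferential safety tests, so no hypothesis test is affected. None of these points puts a non-serious worsening into a TEAE table.

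**Conclusion.** The point holds in this limited form. By the stated rule, a non-serious AE that begins between consent and first application and increases in grade afterwards is not a TEAE, and Tables 14.3.1.1 to 14.3.1.8 omit it unless a site opens a new record or the physical-examination route applies.

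The number of events is unknown because the documents give no rate, and it is probably small. The assumed rates above give about 0.5 to 6 subjects in Cohort 2 and well under one in Cohort 1; they illustrate scale and are not an estimate. What is certain is the direction: the omission can only undercount on-treatment worsening.

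The SAP already deals with the same straddling problem for medications. SAP 9.7 counts a medication that starts before and continues after first application as both prior and concomitant. AEs have no comparable rule. The correction is worth making because it is cheap and concerns the main safety summaries. It does not affect the efficacy analysis.

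**What to change.** 1. In protocol 5.7.1 and 6.3.1 and SAP 6.1.7 and 9.1, use one definition: an AE with onset at or after the first application, or an AE present before it whose CTCAE grade increases at or after it.
2. Make the same change in every footnote that repeats the old rule: the AE table shells, Table 14.3.3.1 and Listing 16.2.7.1. Otherwise the shells will contradict the text.
3. Add one recording rule to protocol 5.7.5: a post-application grade increase of a pre-dose AE is entered with its own start date and grade.
4. State how the two parts work together. The pre-dose entry keeps its pre-dose grade and is not a TEAE. The worsening entry carries the TEAE flag, and its grade, relationship and action taken feed the tables. The worsening is then identifiable and counted once. The clause in the definition covers any case where a site does not make the second entry.

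The cost is wording in four definitions and their footnotes, one entry convention, a little extra data entry and a few more TEAEs counted. No visit or test is added.

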5.7.2 Serious Adverse Event Definition

The definitions and reporting requirements of Health Canada/the Food and Drug Administration (FDA)/ Therapeutic Goods Administration (TGA)/ICH Guidelines for Clinical Safety Data Management, Definitions and Standards for Expedited Reporting, Topic E2A will be adhered to. If any AEs are serious, as defined by ICH Guidelines for Clinical Safety, required procedures will be followed.

All SAEs will be reported to the Sponsor (or delegate) via fax or e-mail within 24 hours of becoming aware of the event, whether or not the serious events are deemed IP-related.

All serious event reporting will adhere to ICH E6: Guideline for Good Clinical Practice and ICH E2A: Clinical Safety Data Management: Definitions and Standards for Expedited Reporting.: The ERB/IRB will be notified of the Alert Reports as per HC, FDA, ICH and the IRB/ERB's policies and procedures. Refer to the Safety Reporting Instructions for SAE reporting.

An SAE is any AE that in the view of either the PI or Sponsor, results in any of the following outcomes: Death, a life-threatening AE, inpatient hospitalization or prolongation of existing hospitalization, a persistent or significant incapacity or substantial disruption of the ability to conduct normal life functions, or a congenital anomaly/birth defect. Important medical events that may not result in death, be life-threatening, or require hospitalization may be considered serious when, based upon appropriate medical judgment, they may jeopardize the subject and

may require medical or surgical intervention to prevent one of the outcomes listed in the above definition. Examples of such medical events include allergic bronchospasm requiring intensive treatment in an emergency room or at home, blood dyscrasias or convulsions that do not result in inpatient hospitalization, or the development of drug dependency or drug abuse.

Life-threatening is defined as an AE that in the view of the PI or Sponsor, places the subject at immediate risk of death. It does not include an AE that, had it occurred in a more severe form, might have caused death.

Hospitalization does not include the following:

- Rehabilitation facilities, hospice facilities or respite care (e.g., caregiver relief)
- Nursing homes or skilled nursing facilities
- Emergency room visits
- Same day surgeries (as outpatient/same day/ambulatory procedures)
- <24 hour admissions for observation or evaluation

Hospitalization or prolongation of hospitalization in the absence of a precipitating, clinical AE is not in itself an SAE. Examples include:

- Admission for treatment of a preexisting condition that did not worsen
- Hospitalizations for cosmetic elective surgery, social, and/or convenience admissions
- Pre-planned treatments or surgical procedures should be noted in the history documentation for the individual subject.
- Diagnostic and therapeutic procedures, such as surgery, should not be reported as AEs; however, the medical condition for which the procedure was performed should be reported if it occurs during the reporting period and meets the definition of an AE. For example, an acute appendicitis that begins during the AE reporting period should be reported as an AE, and the resulting appendectomy should be recorded as treatment of the AE.

Unexpected is defined as an AE that is not listed in the IB or is not listed at the specificity or severity that has been observed; or is not consistent with the risk information described in the general investigational plan or elsewhere in the current study documentation.

If a SAE occurs to a subject on this study, contact the Medical Monitor within one business day of knowledge of event.

5.7.3 Suspected Unexpected Serious Adverse Reaction (SUSAR)

This is defined as a serious adverse reaction, the nature or severity of which is not consistent with the known study treatment information. A serious event or reaction is not defined as a SUSAR when: 'it is serious but expected' or it does not fit the definition of an SAE, whether expected or not.

5.7.4 Safety Review with Subject

At each follow-up visit, subjects will be queried with an open-ended question such as: ‘How have you been feeling since your last visit?’ Additionally, the study staff will review subject diaries and, if it appears that a potential AE was recorded, study staff will query the subject and determine if an AE occurred.

AEs (whether serious or non-serious) and clinically significant abnormal laboratory test value(s) will be evaluated by the PI and treated and/or followed up for up to one month after end of treatment until the symptoms or value(s) return to normal, or acceptable levels, as judged by the PI.

Where appropriate, medical test(s) and/or examination(s) will be performed to document resolution of event(s). Outcome may be classified as resolved, improved, unchanged, worse, fatal or unknown (lost to follow-up).

5.7.5 Adverse Event Reporting

AEs will be collected following informed consent of the subject through subject study completion.

The Investigator will review each event and assess its relationship to investigational product treatment (unrelated, unlikely, possibly, probably, likely). Each sign or symptom reported will be graded on the NIH NCI CTCAE (Version 5.0) toxicity grading scale 5-point severity scale (Grade 1, 2, 3, 4 and 5). The date and time of onset, time relationship to drug dosing, duration, and outcome (resolved, improved, unchanged, worse, fatal, or unknown/lost to follow-up) of each event will be noted.

The relationship of each AE to the investigational product will be assessed using the following definitions:

Unrelated	
 The AE must clearly be caused by the subject’s clinical state, or the study procedure/conditions. Definitely not related to drug. Temporal sequence of AE onset relative to administration of drug not reasonable. Another obvious cause of an AE.
Unlikely	
 Time sequence is unreasonable. There is another more likely cause for an AE.
Possibly	
 Corresponds to what is known about the drug. Time sequence is reasonable. Could have been due to another equally, likely cause.
Probably	
 Is a known effect of the drug. Time sequence from taking drug is reasonable. Ceases on stopping the drug. Cannot be reasonably explained by the known characteristics of the subject’s clinical state.
Likely	
 Is a known effect of the drug (e.g., listed in Physicians' Desk Reference, Compendium of Pharmaceuticals and Specialties, IB). Time sequence from taking drug is reasonable. Event stops upon stopping drug, event returns upon restarting drug.

The following CTCAE toxicity grading scale 5-point severity scale definitions for rating maximum severity will be used:

Grade 1	Mild; asymptomatic or mild symptoms; clinical or diagnostic observations only; intervention not indicated.
Grade 2	Moderate; minimal, local or noninvasive intervention indicated; limiting age-appropriate instrumental activities of daily living.*
Grade 3	Severe or medically significant but not immediately life-threatening; Hospitalization or prolongation of hospitalization indicated; disabling; limiting self-care activities of daily living.** Note: An experience may be severe but may not be serious, e.g., severe headache).
Grade 4	Life-threatening consequences; urgent intervention indicated.
Grade 5	Death related to AE.

Note: A semi-colon indicates 'or' within the description of the grade.

*Instrumental activities of daily living refer to preparing meals, shopping for groceries or clothes, using the telephone, managing money, etc.

**Self-care activities of daily living refer to bathing, dressing and undressing, feeding self, using the toilet, taking medications, and not bedridden.

AEs will be coded using the most current MedDRA[®] version available at the start of the study (e.g., 21.0 or higher).

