2.3 Clinical Studies

This will be the first study of topical ARQ-252 cream in the human population.

Oral administration of SHR0302 has been studied in three Phase 1 pharmacokinetic studies, including two conducted in healthy volunteers and one conducted in subjects with rheumatoid arthritis. Oral administration of SHR0302 has also been studied in a 24-week, Phase 2 study in subjects with rheumatoid arthritis.

2.3.1 Oral Administration: Phase 1

In three Phase 1 pharmacokinetic studies, a total of 94 subjects were exposed to SHR0302 at various dosages and duration. The single maximum dose of exposure in humans was 100 mg, and the longest duration of exposure was 7 days of 10 mg SHR0302 in rheumatoid arthritis patients.

A study on human safety, pharmacokinetics, and pharmacodynamics was conducted on SHR0302 following single dose oral administration in healthy subjects (SHR0302-101). This was a randomized, double blind and placebo-controlled study with six dosage groups of 1, 5, 10, 25, 50 and 100 mg. AEs were reported mainly from the high-dose groups (50 mg and 100 mg) in this single ascending dose study. The most common AEs involved the hematologic system (neutropenia and high lymphocyte count). Adverse reactions included neutropenia in 7 subjects (10.9%), elevated lymphocytes in 6 subjects (9.4%), and leukopenia in 1 subject (1.6%). At the 25 mg dose and below, there was no obvious difference between the active and placebo arms. There were no serious adverse events.

Following single oral dose administration, SHR0302 was rapidly absorbed with median T_{max} values of 1.0 hour across all dose groups. Geometric mean C_{max} values increased 105-fold over the 100-fold increase in dose (1 to 100 mg), demonstrating dose proportional kinetics. Similarly, the geometric mean AUC_{0-24} values increased 107-fold over the same 100-fold increase in dose.

A multiple ascending dose (MAD) study of human safety, pharmacokinetics, and pharmacodynamics was conducted on orally administered SHR0302 in subjects with rheumatoid arthritis (SHR0302-102). This was a randomized, double-blind, and placebo-controlled study with four planned dosage groups of 2, 5, 10 and 25 mg. Each dosage group had 12 subjects, 10 receiving active and 2 receiving placebo. Subjects were dosed for 7 days. The 2, 5, and 10 mg dose groups were completed, for a total of 36 subjects, 30 receiving active drug. No subjects in the 25 mg dose group were enrolled.

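### The three causality categories counted as related all carry a prior-knowledge condition, so a reaction of a new kind to the cream has no clear category and may be under-classified

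*Protocol*

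**What the plan says.** Protocol 5.7.5 asks the investigator to rate each event's relationship to the investigational product as Unrelated, Unlikely, Possibly, Probably or Likely, and lists criteria for each.

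- Possibly begins "Corresponds to what is known about the drug. Time sequence is reasonable" and adds that another cause could be equally likely.
- Probably begins "Is a known effect of the drug. Time sequence from taking drug is reasonable. Ceases on stopping the drug" and adds that the subject's clinical state does not reasonably explain the event.
- Likely begins "Is a known effect of the drug (e.g., listed in", gives the IB as one example of a source, and adds reasonable timing and return of the event on restarting.
- Unlikely and Unrelated rest on unreasonable timing or on another cause.

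The section does not say whether all criteria in a category must be met.

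Expectedness is defined elsewhere. Protocol 5.7.2 says "Unexpected is defined as an AE that is not listed in the IB", and goes on to include events listed at a different specificity or severity. Protocol 5.7.3 defines a SUSAR as a serious adverse reaction "the nature or severity of which is not consistent with the known study treatment information".

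For analysis, SAP 9.1 sets "related = likely related, probably related, or possibly related; unrelated = unlikely related or unrelated". SAP 6.1.8 and 9.1 count a missing relationship as related. Protocol 2.3 states: "This will be the first study of topical ARQ-252 cream in the human population".

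**The concern.** Whether the product caused an event and whether the event was already known are separate questions. A causality scale that asks for prior knowledge gives its lowest ratings to reactions nobody has seen before, whatever the strength of the individual evidence.

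That matters more here than in most trials. Protocol 2.4.2 derives the cream's potential risks from the oral form and from the JAK inhibitor class. Reactions to the topical formulation on eczematous hands are what this study is placed to discover. If such a reaction is rated too low, it moves out of the related counts. If it is serious and new in nature, it may also not be recognised as a SUSAR.

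**Working it through.** No arithmetic applies beyond counting criteria, and the plan states no figure to reproduce. Take one test event: new in nature, reasonable timing, no other cause, resolves on stopping, not re-exposed. Set it against each category in Protocol 5.7.5.

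| Category | SAP 9.1 | Criteria the test event meets | Criteria it fails |
|---|---|---|---|
| Unrelated | unrelated | 0 of 4 | clear other origin; definitely not drug; unreasonable timing; obvious other cause |
| Unlikely | unrelated | 0 of 2 | unreasonable timing; more likely other cause |
| Possibly | related | 1 of 3 (timing) | fit with what is known; equally likely other cause |
| Probably | related | 3 of 4 (timing, stops on stopping, not explained by clinical state) | known effect |
| Likely | related | 1 of 3 (timing) | known effect; return on restarting (untested) |

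Probably is the closest match, and the known-effect condition is the only thing that excludes it. With a positive rechallenge, the same would be true of Likely.

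The result depends on how the criteria combine, which the protocol leaves open.

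1. **All required.** The test event fits none of the five categories.
2. **Any one suffices.** Reasonable timing appears in all three related categories, so every well-timed event would be Possibly, Probably and Likely at once. The scale then separates nothing. Protocol 5.7.5 states an or-rule for its severity grades (the semi-colon note) but none for causality.
3. **Guidance for judgement.** The event can be rated, but the knowledge criterion still pulls the rating down, and investigators may differ.

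Two examples show that the gap is practical.

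- Protocol 4.10 foresees suspected allergic contact dermatitis and encourages patch testing. Protocol 2.2 reports that ARQ-252 was not a skin sensitiser in the local tolerance studies. Contact allergy to the cream therefore fits poorly with what is known about the drug.
- The knowledge criteria speak of the drug, while the rating concerns the investigational product. A reaction to an excipient, including in either vehicle arm, is not an effect of the drug at all.

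**SUSAR routes.** A reaction unexpected in nature is blocked under Probably and Likely if the criteria are required. It passes under Possibly only if it fits existing knowledge such as the mechanism or the oral data. A reaction unexpected in severity or specificity passes under all three.

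**Tables.** SAP 13.1.3.1 and 13.1.3.2 plan 8 + 3 = 11 adverse event tables. Four depend on relationship (14.3.1.4, 14.3.1.6, 14.3.1.8, 14.3.2.3), and 14.3.1.1 has two related rows. The other 11 − 5 = 6 do not use relationship. An event rated Unlikely would move to the not-related line of 14.3.1.4, and of 14.3.2.3 if serious. It would drop out of 14.3.1.8, and out of 14.3.1.6 if it led to stopping study drug.

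**The case against.** The case on the other side corrects several things that a reader might infer.

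- **That every related category demands a known effect.** Only Probably and Likely do. Possibly asks for correspondence with what is known, which an unlisted event can meet if it fits the mechanism or the oral data. Possibly is also the threshold for being counted as related. This stands. It leaves a ceiling at Possibly for such events, and nothing clear for an event that fits no existing knowledge.
- **That a SUSAR cannot arise.** Protocol 5.7.2 and 5.7.3 also define unexpectedness by severity or specificity, so a known effect in a worse form can be related, serious and unexpected. Nor does 5.7.3 tie an adverse reaction to the 5.7.5 categories. This stands, and limits the point to reactions new in nature.
- **That new events are forced into unrelated.** The test event fits Unlikely and Unrelated no better, and nothing directs the investigator there. A strict all-required reading is also awkward: Likely would always need a rechallenge, and Unlikely would need both poor timing and another cause. This stands. The defect is a gap in the scale, not a forced rating.
- **That prior knowledge is oral only.** Protocol 2.2 reports dermal studies in mice and minipigs and local tolerance work, and exclusion criterion 15 names the excipients. This stands.

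The safeguards are real but partial. All SAEs go to the sponsor within 24 hours regardless of causality (5.7.2), but that covers serious events only. The documents describe no separate sponsor causality assessment, although 5.7.2 refers to Safety Reporting Instructions that are not available here. Protocol 4.10 sends any condition possibly related to the product to the Medical Monitor, with no known-effect condition. Local tolerability is summarised without attribution, and six adverse event tables ignore relationship. The missing-as-related rule helps only if the rating is left blank, whereas 5.7.5 asks for one on every event.

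**Conclusion.** The point holds in a limited form. Each category counted as related contains a prior-knowledge condition, which confuses causality with expectedness. A reaction that is new in nature, well timed, without another cause and resolving on stopping has no clear category. It cannot be rated Probably or Likely if the known-effect criterion is taken as required, which the protocol neither states nor denies.

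The effect is possible under-classification in four tables and two rows of a fifth, and in recognising SUSARs unexpected in nature. How many events this would touch cannot be estimated from the documents. Reporting of SAEs to the sponsor and the tables that do not use relationship are unaffected. The documents do not support saying that SUSARs are excluded by definition, or that new events must be counted as unrelated.

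**What to change.** In Protocol 5.7.5, remove prior knowledge as a required condition from Possibly, Probably and Likely. Have relationship to the investigational product, vehicle excipients included, judged on timing, dechallenge or rechallenge, and alternative causes. State how the criteria in each category combine, so that every event has a category. Add that expectedness is assessed separately against the IB, consistent with 5.7.2 and 5.7.3. The SAP 9.1 mapping can stay as it is.

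The cost is protocol wording and CRF completion guidance. Somewhat more events will be called related, which is acceptable in a first human study of a topical product with vehicle arms for comparison.
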